### **6.2.2 Early Termination Visit**

For subjects who discontinue the Induction Phase and the Maintenance Phase of the study prematurely for any reason (ie, subjects who do not complete Week 48) or enter the OLE Phase during the Maintenance Phase (if a subject meets the rescue criteria detailed in [Section 6.4.2.10](#), the subject can enter the OLE Phase), every attempt should be made to complete the assessments detailed in the ET Visit conducted as close as possible to the time of study discontinuation or of the visit determining entrance to the OLE Phase from the Maintenance Phase. The ET Visit should be completed within 2 weeks after the final CC-93538 dose. If study discontinuation or the visit determining entrance to the OLE Phase from the Maintenance Phase occurs at the regularly scheduled visit (eg, Induction Phase Week 12 or Maintenance Phase Week 32), the ET Visit and all corresponding ET Visit procedures should be conducted ([Table 4](#) and [Table 5](#)). In addition, subjects who discontinue the study should return for the Safety Follow-up Visit ([Section 6.3.1](#)). Subjects who complete the Induction Phase Week 16 Visit but do not continue in the Maintenance Phase or the OLE Phase should complete the Week 16/ET Visit and return for the Interim 8-week and Final 16-week Safety Follow-up Visits at Week 23 and Week 31, respectively ([Section 6.3.1](#)). Subjects who complete the Induction Phase and enter the OLE Phase should complete the Week 16/ET Visit; these subjects do not need to return for the 2 Safety Follow-up Visits. Assessments conducted at the Week 16 Visit do not need to be repeated. Subjects who do not complete

\* Note that these samples do not need to be a pre-dose draw unless the subject is expected to dose later that day.

\*\* Note that EGD is required at EGE Flare Assessment Visits to determine if use of rescue therapy is clinically indicated. Alternatively, if an endoscopy is conducted as part of an emergency department visit or hospitalization for the EGE flare, medical record source data should be collected for the EGE Flare Assessment Visit EGD requirement. In addition, all attempts should be made to collect biopsy samples, and these samples should be sent to the central reader for histologic analysis.

Maintenance Phase Week 48 but enter the OLE Phase ([Section 3.1.6](#)) do not need to return for the 2 Safety Follow-up Visits. Subjects who complete the Maintenance Phase Week 48 but do not continue in the OLE Phase should return for the Interim 8-week and Final 16-week Safety Follow-up Visits at Week 55 and Week 63, respectively. For subjects who are discontinuing the study prematurely due to an EGE flare, ET procedures performed at the EGE Flare Assessment Visit do not need to be repeated.

The following evaluations will be performed as specified in (Table 4 and Table 5):

\* Note that EGD is not required for ET Visits occurring before Week 8 in the Induction Phase or before Week 24 in the Maintenance Phase.

Refer to [Section 6.4](#) for a description of the efficacy assessments conducted throughout the study.

### 6.3 Follow-up Period

#### 6.3.1 Safety Follow-up (Interim 8-week and Final 16-week)

All subjects will be followed for 16 weeks after the last dose of IP or until the Final Safety Follow-up Visit, whichever is longer, for AE reporting, as well as SAEs made known to the investigator at any time thereafter that are suspected of being related to IP, as described in [Section 10.2.3](#).

In the Induction Phase, subjects who discontinue from the study prior to completing Week 16, or subjects who complete Week 16 and do not enter the Maintenance Phase or the OLE Phase will return for an Interim and a Final Safety Follow-up Visit at 8 and 16 weeks, respectively, after final IP administration (at Week 23 and Week 31 for subjects completing the Induction Phase) for the assessment of safety and clinical status after exiting the study. However, subjects who are permanently discontinued from IP and continue study participation in order to complete safety and efficacy assessments in the phase of the study that permanent discontinuation from IP occurs (according to [Section 11.1](#)) will return for the Interim and Final Safety Follow-up Visits 8 and 16 weeks after their last study visit instead of their last dose of IP (eg, Week 16 or the ET Visit). Assessments should be performed in accordance with the Table of Events ([Table 4](#)). Subjects who continue participation in the Maintenance Phase or the OLE Phase will not return for the 2 Safety Follow-up Visits.

In the Maintenance Phase, subjects who discontinue from the study prior to completing Week 48 but do not enroll in the OLE Phase or complete Week 48 but do not enroll in the OLE Phase will also return for an Interim and a Final Safety Follow-up Visit at 8 and 16 weeks, respectively after final IP administration (at Week 55 and Week 63 for completers of the Maintenance Phase) for the assessment of safety and clinical status after exiting the study. However, subjects who are permanently discontinued from IP and continue study participation in order to complete safety and efficacy assessments in the phase of the study that permanent discontinuation from IP occurs (according to [Section 11.1](#)) will return for the Interim and Final Safety Follow-up Visits 8 and 16 weeks after their last study visit instead of their last dose of IP (eg, Week 48 or the ET Visit). Assessments to be performed are presented in the Table of Events ([Table 5](#)). Subjects who continue participation in the OLE Phase will not return for the 2 Safety Follow-up Visits.

In the OLE Phase ([Section 6.3.2](#)), all subjects should return for an Interim and a Final Safety Follow-up Visit at 8 and 16 weeks, respectively after final IP administration. Assessments to be performed are presented in the Table of Events ([Table 6](#)).

The following evaluations will be performed as specified in [Table 4](#), [Table 5](#) and [Table 6](#):

- Concomitant therapy
- Assessment of AEs/SAEs (monitored through 16 weeks after the last dose of IP or the Final Safety Follow-up Visit, whichever is longer)
- Hematology, chemistry, and urinalysis

- Pregnancy test (only for FCBP)
- Physical examination  
[REDACTED]
- Vital signs
- Serum antibodies to CC-93538
- Serum CC-93538 PK assessment
- Weekly Izumo Scale questionnaire at least for the prior week (7 days) period preceding each of the 2 Safety Follow-up Visits (for Safety Follow-up of the Induction Phase and the Maintenance Phase)
- EGID Severity Score (for Safety Follow-up of the Induction Phase and the Maintenance Phase)  
[REDACTED]  
[REDACTED]  
[REDACTED]

Refer to [Section 6.4](#) for a description of the efficacy assessments conducted throughout the study.

### **6.3.2      *Open-label Long-term Extension (OLE) Phase***

The OLE Day 1/Baseline assessments shown in [Table 6](#) will be completed prior to the first dose of CC-93538 in the OLE Phase. OLE Day 1/Baseline refers to any visit during which OLE baseline assessments are obtained, including the following visits from: Induction Phase Week 16 Visit or the Maintenance Phase Week 48 Visit, or the ET Visit during the Maintenance Phase. Transition to the OLE Phase should occur for most subjects on the same day as the Induction Phase Week 16 Visit, the Maintenance Phase Week 48 Visit or the ET Visit during the Maintenance Phase. Subjects entering the OLE Phase will not complete the Safety Follow-up Visits after the Induction Phase or the Maintenance Phase. Subjects will not be eligible to enroll in the OLE Phase and receive CC-93538 on OLE Day 1 if there will be a delay of > 21 days from dosing in the final Induction Visit or the final dosing in the Maintenance Phase. The investigator will review all available information to confirm that the subject continues to meet all study enrollment criteria and complete the additional Day 1 activities for confirmation of eligibility.

The following evaluations/activities will be performed as specified in [Table 6](#):

- Confirm eligibility: If the results of the gastric/duodenal eos count will be disclosed during the Induction Phase, the subject is to be discontinued from the study and will not be allowed to enter the OLE Phase.
- The OLE baseline assessments will include those conducted for the Induction Phase Week 16 Visit, Maintenance Phase Week 48 Visit or Maintenance Phase ET Visit, as applicable. Additional OLE baseline assessments not performed at the final Induction Phase Visit (Week

16), Maintenance Phase Visit (Week 48), or Maintenance Phase ET Visit should be conducted at the OLE Day 1 Visit (or repeated in the case that the assessment requires re-evaluation on the same day just prior to dosing [eg, pregnancy test]) in accordance with the schedule of events ([Table 6](#)). Subjects will not be allowed to enroll in the OLE study and receive CC-93538 on Day 1 if there will be a delay of > 21 days from final dosing in the Induction Phase or the Maintenance Phase unless discussed with the Medical Monitor.

- The EGD procedure should not be repeated at the OLE Day 1 Visit, as long as this assessment was conducted at the final Induction Phase Visit (Week 16), Maintenance Phase Visit (Week 48), or Maintenance Phase ET Visit.
- If OLE Day 1 is not on the same day as the final Induction Phase (Week 16), Maintenance Phase (Week 48) Visit or ET Visit during the Maintenance Phase, a urine (or serum)  $\beta$ -hCG pregnancy test (FCBP only) must be performed on OLE Day 1 and the results reviewed on OLE Day 1 prior to the first open-label OLE CC-93538 dose. A negative pregnancy test result must be obtained for these subjects prior to dosing. If the urine pregnancy test result is positive but this is believed to be a false positive, the site may perform a serum pregnancy test at the local laboratory to confirm pregnancy status.
- If subjects had an EGD performed for an EGE flare assessment during the Induction (prior to Week 16) or Maintenance (prior to Week 48) Phases, an EGD will also be performed at Week 16 or Week 48, respectively. However, an exception will be made if in the investigator's judgment the EGE flare assessment occurred too close to Week 16 or Week 48 such that it is considered unsafe to perform another EGD within this short interval. In these cases, a discussion with the Medical Monitor will take place well in advance of the OLE Day 1 Visit.

After baseline assessments have been completed, eligible subjects will receive CC-93538 360 mg in an open-label manner. The first 3 SC weekly doses will be administered in the clinic. Subjects will remain in the clinic for at least 30 minutes following dosing for observation.

If a subject weighing  $\geq$  30 kg and  $<$  40 kg enters the OLE Phase from Week 16 of the Induction Phase or during Maintenance Phase, the first 3 weekly SC doses will be administered in the clinic with confirmation of concomitant medications and AEs, and those subjects will remain in the clinic for at least 1 hour following dosing for observation and be monitored every 2 weeks by the site staff by telephone (but not limited to telephone) between regularly scheduled visits until OLE Week 16 (ie, OLE Week 6 [Day 43  $\pm$  3 days], OLE Week 10 [Day 71  $\pm$  3 days], OLE Week 12 [Day 85  $\pm$  3 days], and OLE Week 14 [Day 99  $\pm$  3 days]).

Subsequent visits, assessments and procedures will be performed as shown in [Table 6](#).

Following OLE Day 1, in the first year of the OLE Phase (OLE Treatment Period Year 1), subjects will attend study visits through Week 48. After completion of Week 48 plus an additional 4 weeks in the OLE Treatment Phase (that is, after Week 52 in the OLE Phase), subjects will continue on into the second year of the OLE (Year 2 and beyond). During Year 2 and beyond, subjects will attend study visits every 13 weeks ( $\pm$  14 days) for a total of four quarterly study visits each year within a 52-week per year format. For each year of participation after Week 52, the Quarterly 1 Visit, Quarterly 2 Visit, Quarterly 3 Visit, and Quarterly 4 Visit will be completed. The Quarterly 2 and 4 Visits will include additional assessments not included in Quarterly 1 and 3 Visits. The time points for these visits are as follows:

- Quarterly 1 Visits will occur at the end of the first quarter of each year after Week 52 (Year x + Week 13 [ $\pm$  14 days])
- Quarterly 2 Visits will occur at the mid-point of each year after Week 52 (Year x + Week 26 [ $\pm$  14 days])
- Quarterly 3 Visits will occur at the end of the third quarter of each year after Week 52 (Year x + Week 39 [ $\pm$  14 days])
- Quarterly 4 Visits will occur at the end of each year after Week 52 (Year x + Week 52 [ $\pm$  14 days])

For example, for the Quarterly 1 Visit occurring at Week 13, where Year x is Year 2, the visit will occur at 52 Weeks plus 13 Weeks = Week 65, and for the Quarterly 4 Visit, where Year x is Year 2, the visit will occur at 52 Weeks plus 52 Weeks = Week 104.

The following evaluations will be performed during the OLE Phase as specified in the [Table 6](#):

- Concomitant therapy
- Assessment of AEs/SAEs (monitored through 16 weeks after the last dose of IP or the Final Safety Follow-up Visit, whichever is longer). Refer to [Section 10](#) for definitions of AEs/SAEs, monitoring, and reporting. In addition, [REDACTED]/PFS device failures or malfunctions should be captured, and device-related AEs should also be collected.
- Hematology, chemistry, and urinalysis
- Pregnancy test (only for FCBP)
- Physical examination

- Vital signs
- Serum antibodies to CC-93538
- Serum CC-93538 PK assessment

[figure not shown]
- Weekly Izumo Scale questionnaire
- EGID Severity Score

- [REDACTED]
- EGD with tissue biopsies\*
- [REDACTED]
- CC-93538 administration

Telephone call reminders may take place before the 28-day collection period for daily assessment preceding the OLE Week 24, OLE Week 36 and OLE Week 48 endpoint assessments (ie, just prior to OLE Weeks 20, 32 and 44), if applicable. A telephone contact may be made at other time points as part of ongoing surveillance.

Refer to [Section 6.4](#) for a description of the efficacy assessments conducted throughout the study.

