Following a 4-week Screening Period, subjects meeting all inclusion criteria and none of the exclusion criteria will be eligible for enrollment in the 16-week Induction Phase. Subjects (N = approximately 45) will be randomized (2:1) to receive CC-93538 360 mg subcutaneously (SC) once weekly or matching placebo, in a double-blind fashion for the 16 weeks of the Induction Phase. At the beginning of the Maintenance Phase, subjects who are randomized to receive CC-93538 360 mg SC once weekly in the Induction Phase will be re-randomized (1:1) to CC-93538 360 mg SC once weekly or CC-93538 360 mg SC once every other week, and subjects who are randomized to receive matching placebo in the Induction Phase will continue placebo in the Maintenance Phase. A double-blind fashion will be kept in the Maintenance Phase. Subjects will be required to have weekly symptom scores of  $\geq 4/15$  for any of Gastric Pain Symptom domain, Stomach Heaviness Symptom domain, and /or Diarrhea Symptom domain as assessed by the patient-reported outcome (PRO) questionnaire (referred to as Izumo Scale) with electronic device over the 2 consecutive weeks before the investigational product (IP) administration on Day 1 and has histologic evidence of EGE with  $\geq 30$  eos/hpf in at least 5 hpf in the stomach and/or  $\geq 30$  eos/hpf in at least 3 hpf in the duodenum; both assessments will be conducted while on stable concomitant corticosteroid therapy (up to 10 mg/day as prednisone). Peak gastric/duodenum eos count will be confirmed by a centrally read histological assessment of an esophagogastroduodenoscopy (EGD) specimen. Subjects weighing  $\geq 30$  kg will be enrolled in this study. Currently, there is no administration experience of CC-93538 360 mg once weekly in subjects weighing  $< 40$  kg. Careful and close safety monitoring should be implemented for this population. For subjects weighing  $\geq 30$  kg and  $< 40$  kg, the first 3 weekly SC doses will be administered in the clinic with confirmation of concomitant medications and AEs, and those subjects will remain in the clinic for at least 1 hour following dosing for observation and be monitored every 2 weeks by the site staff by telephone (but not limited to telephone) between regularly scheduled visits until Week 16 (ie, Week 6 [Day 43  $\pm$  3 days], Week 10 [Day 71  $\pm$  3 days], and Week 14 [Day 99  $\pm$  3 days]).

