## **Length of Study**

The maximum duration of subject participation in the Screening Period, Induction and Maintenance Phases is approximately 72 weeks, including the Interim and the Final Safety Follow-

up Visits. Subjects will participate for up to 4 weeks in the Screening Period (the screening EGD may be completed up to 8 weeks prior to Day 1), 16 weeks in the Induction Phase, and 32 weeks in the Maintenance Phase of the study. Subjects completing the Maintenance Phase who do not continue IP administration in the OLE Phase will complete the Interim and the Final Safety Follow-up Visits (at 8 and 16 weeks) after final IP administration.

Subjects entering the OLE Phase at Induction Phase Week 16, during the Maintenance Phase or at Maintenance Phase Week 48 will receive weekly doses of CC-93538 during the OLE Phase for a minimum of 2 years or as long as they continue to participate while the study is active, will complete an Early Termination Visit or an End of Treatment Visit within 2 weeks after the final dose, and complete the two Safety Follow-up Visits at 8 and 16 weeks after the final dose. Subjects may participate in the OLE Phase as early as 16 weeks after beginning enrollment in the Induction Phase or as late as following Week 48 of the Maintenance Phase. Individual subject participation in the OLE Phase may be a minimum of 2 years but may extend for a longer duration, provided the subject does not withdraw from the OLE Phase prior to Year 2 of the OLE. The terms “this study” in this protocol will automatically be replaced with “post-marketing clinical study” on and after the date of marketing approval in Japan.

The End of Trial is defined as either the date of the last visit of the last subject to complete the post-treatment follow-up (the Final Safety Follow-up Visit), or the date of receipt of the last data point from the last subject that is required for primary, secondary [REDACTED] analysis, as prespecified in the protocol, whichever is the later date.

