### **3.1.2      Induction Phase**

Following a 4-week Screening Period, subjects meeting all inclusion criteria and none of the exclusion criteria will be eligible for enrollment in the Induction Phase. Approximately 45 subjects 12 to 75 years of age, inclusive, with a diagnosis of EGE and with symptoms of EGE will be randomized 2:1 to receive CC-93538 360 mg SC once weekly (N = approximately 30) or matching placebo (N = approximately 15), in a double-blind fashion for 16 weeks. Subjects will be required to have weekly symptom scores of  $\geq 4/15$  for any of Gastric Pain Symptoms domain, Stomach Heaviness Symptoms domain and /or Diarrhea Symptoms domain, as assessed by the Izumo Scale with electronic device over the 2 consecutive weeks before baseline (assessed on Day 1), and histologic evidence of EGE with  $\geq 30$  eos/hpf in at least 5 hpf in the stomach and/or  $\geq 30$  eos/hpf in at least 3 hpf in the duodenum. Both assessments will be conducted while on stable background therapy. Peak gastric/duodenum eos count will be confirmed by the central reader.

Subjects weighing  $\geq 30$  kg will be enrolled in this study. Currently, there is no administration experience of CC-93538 360 mg once weekly in subjects weighing  $< 40$  kg. Careful and close safety monitoring (eg, for hypersensitivity reaction) should be considered for this population. For subjects weighing  $\geq 30$  kg and  $< 40$  kg, the first 3 weekly SC doses will be administered in the

clinic, with confirmation of concomitant medications and AEs, and those subjects will remain in the clinic for at least 1 hour following dosing for observation, and be monitored every 2 weeks by the site staff by telephone (but not limited to telephone) between regularly scheduled visits until Week 16 (ie, Week 6 [Day 43 ± 3 days], Week 10 [Day 71 ± 3 days], and Week 14 [Day 99 ± 3 days]).

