### **3.1.3 Maintenance Phase**

After completion of Week 16 of the Induction Phase, eligible subjects will continue participation and enter the Maintenance Phase if none of the conditions disqualifying subjects from eligibility have been met as described in [Section 3.1.6](#). A placebo-controlled Maintenance Phase will allow for a determination of persistence of treatment effect and the overall long-term efficacy of CC-93538.

The Maintenance Phase treatment arms include CC-93538 360 mg SC once every week, CC-93538 360 mg SC once every other week, and matching placebo. Subjects who are randomized to receive CC-93538 360 mg SC once weekly in the Induction Phase will be re-randomized (1:1) to CC-93538 360 mg SC once weekly or CC-93538 360 mg SC once every other week at the beginning of the Maintenance Phase, and subjects who are randomized to receive matching placebo in the Induction Phase will continue placebo in the Maintenance Phase. A double-blind fashion will be kept in the Maintenance Phase.

If the reduction of EGE-related symptoms is observed at/after Week 16 (in the Maintenance Phase), the investigator should begin tapering the dosage regimen of concomitant corticosteroid treatment after Week 16. The dose reduction should be 2.5 mg/week (as the equivalent of prednisone). If the symptoms worsen after tapering of the dosage regimen of concomitant

corticosteroid treatment, the dose can be increased until it is the same as the baseline dose at the Induction Phase.

Subjects who complete Week 48 of the Maintenance Phase have 2 options:

1. to enter the Open-label Long-term Extension Phase (Section 3.1.4)
2. to return for an Interim and a Final Safety Follow-up Visit at 8 and 16 weeks, respectively, after the last dose of IP (at Week 55 and Week 63 for study completers) ([Section 3.1.5](#))

Subjects with a worsening of EGE symptoms (described in [Section 6.4.2.10](#)) during the Maintenance Phase will be required to complete the EGE Flare Assessment Visit per the Table of Events ([Table 5](#)). The subjects will need to discontinue participation in the Maintenance Phase and may be eligible to enter the OLE Phase. Details are described in Section 3.1.6.

Clinical laboratory tests, vital signs, physical examinations [REDACTED]  

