Study Procedures	Base-line a	Open-label Long-term Extension Period Year 1							Open-label Long-term Extension Period Year 2 and Beyond b				EGE Flare Assessment Visit c	OLE-ET/ EoT Visit d	Interim 8-week Safety Follow-up Visit	Final 16-week Safety Follow-up Visit	
		OLE Visit 1 a, e	OLE Visit 2 e	OLE Visit 3 e	OLE Visit 4 e	OLE Visit 5	OLE Visit 6	OLE Visit 7	OLE Q1 Visits	OLE Q2 Visits	OLE Q3 Visits	OLE Q4 Visits					
Visit Label	OLE Visit 1 a, e	OLE Visit 2 e	OLE Visit 3 e	OLE Visit 4 e	OLE Visit 5	OLE Visit 6	OLE Visit 7	OLE Q1 Visits	OLE Q2 Visits	OLE Q3 Visits	OLE Q4 Visits						
Visit Week (Window)	OLE Day 1	OLE Week 4 (Day 29±3d)	OLE Week 8 (Day 57±7d)	OLE Week 16 (Day 113±7d)	OLE Week 24 (Day 169±7d)	OLE Week 36 (Day 253±7d)	OLE Week 48 (Day 337±7d)	End of Q1 (Year x +Wk 13 [±14d])	Mid-point of Year (Year x +Wk 26 [±14d])	End of Q3 (Year x +Wk 39 [±14d])	End of Year (Year x +Wk 52 [±14d])		Within 2 weeks After Final Dose	8 Weeks After Final Dose (±7d)	16 Weeks After Final Dose (±7d)		
Confirm eligibility	X	-	-	-	-	-	-	-	-	-	-		-	-	-	-	
Concomitant therapy	X	X	X	X	X	X	X	X	X	X	X		X	X	X	X	
AEs/SAEs	X	X	X	X	X	X	X	X	X	X	X		X	X	X	X	
Hematology and chemistry f	X	X	X	X	X	X	X	X	X	X	X		X	X	X	X	
Urinalysis f (pre dose)	X	X	-	-	X	-	X	-	X	-	X		X	X	X	X	
Urine pregnancy test (FCBP only) g	X	X	X	X	X	X	X	X	X	X	X		-	X	X	X	
Physical examination h	X	X	X	X	X	X	X	X	X	X	X		-	X	X	X	

**Table 6:** Table of Events for the Open-label Long-term Extension (OLE)

Study Procedures	Base-line a	Open-label Long-term Extension Period Year 1							Open-label Long-term Extension Period Year 2 and Beyond b				EGE Flare Assessment Visit c	OLE-ET/ EoT Visit d	Interim 8-week Safety Follow-up Visit	Final 16-week Safety Follow-up Visit
		OLE Visit 1 a, e	OLE Visit 2 e	OLE Visit 3 e	OLE Visit 4 e	OLE Visit 5	OLE Visit 6	OLE Visit 7	OLE Q1 Visits	OLE Q2 Visits	OLE Q3 Visits	OLE Q4 Visits				
Visit Label	OLE Visit 1 a, e	OLE Visit 2 e	OLE Visit 3 e	OLE Visit 4 e	OLE Visit 5	OLE Visit 6	OLE Visit 7	OLE Q1 Visits	OLE Q2 Visits	OLE Q3 Visits	OLE Q4 Visits	EGE Flare Assessment Visit c	Within 2 weeks After Final Dose	8 Weeks After Final Dose	16 Weeks After Final Dose	

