b After completion of Week 48 (OLE Visit 7) plus an additional 4 weeks in the OLE Phase (that is, after Week 52 of the OLE Phase), subjects will continue on into the second year of the OLE Phase (OLE Year 2 and beyond). During OLE Year 2 and beyond, subjects will attend study visits every 13 weeks ( $\pm$  14 days) for a total of four quarterly study visits each year within a 52-week per year format. For each year of participation after Week 52, the Quarterly 1 Visit, Quarterly 2 Visit, Quarterly 3 Visit, and Quarterly 4 Visit will be completed. The Quarterly 2 and 4 Visits include additional assessments not included in the Quarterly 1 and 3 Visits.

c An EGE Flare Assessment Visit should be scheduled as close as possible to the time when an EGE flare is suspected.

d Subjects who discontinue study treatment at any time during the OLE will be asked to complete either an OLE-ET Visit, if discontinuation occurs before the Quarterly 4 Visit at the end of OLE Year 2 (OLE Week 104), or an OLE-EoT Visit, if discontinuation occurs at or after the Quarterly 4 Visit at the end of OLE Year 2 (OLE Week 104). The visit will occur within 2 weeks after the final dose of CC-93538.

e If subject weighing  $\geq$  30 kg and  $<$ 40 kg enters the OLE Phase from Week 16 of the Induction Phase or during the Maintenance Phase, the first 3 weekly SC doses will be administered in the clinic with confirmation of concomitant medications and AEs, and those subjects will remain in the clinic for at least 1 hour following dosing for observation and will be monitored every 2 weeks by the site staff by telephone (but not limited to telephone) between regularly scheduled visits until OLE Visit 4 (OLE Week 16) (ie, OLE Week 6 [Day 43  $\pm$  3 days], OLE Week 10 [Day 71  $\pm$  3 days], OLE Week 12 [Day 85  $\pm$  3 days], and OLE Week 14 [Day 99  $\pm$  3 days]).

[figure not shown]
f Pre-dose assessment, except for the OLE-ET/EoT Visit, 2 Safety Follow-up Visits and the EGE Flare Assessment Visit (if applicable).

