### **7.2.5     *Instructions for IP Administration***

The SC doses should be administered as described in the Instructions for Use document, avoiding any blood vessels, thickened or tender skin, scars, fibrous tissue, stretch marks, bruises, redness, nevi, or other skin imperfections. Refer to the Pharmacy Manual and Instructions for Use for additional specifications regarding administration, including guidance regarding anatomical locations for injection and rotation of the injection site.

An overdose is any dose of IP given to a subject or taken by a subject that exceeds the dose described in the protocol. There is no information regarding overdose with CC-93538. Any overdose, with or without associated AEs, must be promptly reported to the Medical Monitor. See [Section 10.1](#).

Doses that do not align with required study visits may be administered either in the clinic by study personnel or at the subject's home through self or caregiver administration or by a visiting home health nurse (once the subject has completed the first 3 required in-clinic doses).

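### The extra open-label safety monitoring for subjects of 30 to <40 kg omits Week 48 completers, including placebo completers taking CC-93538 for the first time

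*Combined protocol and SAP*

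**What the plan says.** Three routes lead into the OLE. The Protocol Summary (Length of Study) lists them side by side: "Subjects entering the OLE Phase at Induction Phase Week 16, during the Maintenance Phase or at Maintenance Phase Week 48". Sections 3.1.4 and 6.2 also treat Week 48 entry as distinct from entry during Maintenance.

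The low-weight rule names two of the three. Section 6.3.2 applies it when a subject of 30 to <40 kg "enters the OLE Phase from Week 16 of the Induction Phase or during Maintenance Phase". Table 6 footnote e has the same limit: "enters the OLE Phase from Week 16 of the Induction Phase or during the Maintenance Phase, the first 3 weekly SC doses". The rule requires:

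- the first three doses in clinic, each followed by at least 1 hour of observation;
- confirmation of adverse events and concomitant medication;
- site contacts at OLE Weeks 6, 10, 12 and 14.

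The reason for special care is given in Section 3.1.2: "Currently, there is no administration experience of CC-93538 360 mg once weekly in subjects weighing" less than 40 kg. The Protocol Summary (Study Design) adds: "Careful and close safety monitoring should be implemented for this population".

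Under Section 3.1.3, "subjects who are randomized to receive matching placebo in the Induction Phase will continue placebo in the Maintenance Phase". Every OLE entrant then receives 360 mg weekly. The general rule in Section 7.2.4, which applies to all entrants, is three in-clinic doses with at least 30 minutes of observation after each.

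**The concern.** The stated ground for the extra measures is body weight and the lack of experience with this dose below 40 kg. A low-weight placebo completer fits that ground exactly: the first exposure to the drug is OLE Day 1. The low-weight monitoring this subject had in Induction took place on placebo and says nothing about tolerance of CC-93538. Yet the rule covers an active-arm subject of the same weight who enters at Week 16 with 16 weeks of exposure, and does not cover this one.

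All Week 48 completers in the weight band are left out. Under 2:1 randomization with equal completion, about two thirds of them would have had active drug; the drug-naive remainder are the main worry. What is at stake is subject safety only.

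**Working it through.** **Routes against coverage**

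| OLE entry route | Low-weight rule applies? |
|---|---|
| Induction Week 16 | Yes |
| During Maintenance (severe flare or worsening) | Yes |
| After Maintenance Week 48 | Not named |

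The Protocol Summary and Section 6.2 list the second and third routes as separate items, so the wording for the second cannot be assumed to include the third. No other visible text requires the measures at Week 48 entry.

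**What the rule does.** In Induction, visits at Weeks 4, 8, 12 and 16 plus low-weight contacts at Weeks 6, 10 and 14 give a contact every two weeks from Week 4. In the OLE, visits at Weeks 4, 8 and 16 plus contacts at Weeks 6, 10, 12 and 14 give the same weeks. The OLE rule therefore reproduces the Induction schedule.

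**Observation over the first three doses.** General rule: 3 × 30 = 90 minutes. Low-weight rule: 3 × 60 = 180 minutes.

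**Contact gap.** Table 6 puts OLE Week 8 at Day 57 ± 7 and the next visit at "OLE Week 16 (Day 113±7d").

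- Without the rule: 113 − 57 = 56 days. Shortest: (113 − 7) − (57 + 7) = 42. Longest: (113 + 7) − (57 − 7) = 70.
- With contacts at Days 71, 85 and 99 (each ± 3): 14 days nominal. Longest: 74 − 50 = 24 at the start and 120 − 96 = 24 at the end.

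**Doses in the gap.** Weeks 9 to 15 = 7 weekly doses. Section 7.2.5 allows these at home: "Doses that do not align with required study visits may be administered either in the clinic by study personnel or at" the subject's home.

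**How many subjects.** The documents do not say, so this is assumption only. Let n subjects be enrolled in the band (0 to 6), one third of them on placebo, with a fraction c completing Week 48 (0.5 to 0.9).

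- Expected placebo completers = n × (1/3) × c, from 0 to 6 × (1/3) × 0.9 = 1.8.
- Chance of at least one = 1 − (1 − c/3)^n:

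| n | c = 0.5 | c = 0.9 |
|---|---|---|
| 0 | 0% | 0% |
| 1 | 17% | 30% |
| 3 | 42% | 66% |
| 6 | 67% | 88% |

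A second set of assumptions, 10 to 15 placebo completers with 2% to 15% of them under 40 kg, gives 10 × 0.02 = 0.2 to 15 × 0.15 = 2.25 expected. The chance of at least one is then 1 − 0.98^10 = 18% to 1 − 0.85^15 = 91%. The two ranges show only that the answer depends on unknown inputs.

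**The case against.** The limit could be deliberate. Subjects entering at Week 16 or during Maintenance mostly do so because of a severe flare or worsening, perhaps on rescue therapy, while Week 48 completers are the more stable group. The same wording in two places fits a choice as well as a slip. However, the plan does not give this reason, and it ties the special care to lack of experience below 40 kg, which does not depend on route.

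Week 48 entrants are also not unprotected. They have three in-clinic doses, visits at OLE Weeks 4, 8 and 16, the option of longer observation (Section 7.2.4) or extra calls (Section 6.3.2), encouragement to report illness, and safety-committee review. Subjects who have difficulty self-injecting are dosed on site or by a home nurse. This is true and narrows the gap. But these protections are general, optional or started by the subject, whereas the measures on the other two routes are mandatory.

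Three points stand:

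- Section 3.1.2 says close monitoring should be considered, which is softer than the Protocol Summary. Both nevertheless make the Induction measures mandatory.
- The probabilities rest on assumption. Placebo subjects who do not improve may leave earlier by a covered route, since Section 6.4.2.10 counts at least four weeks without change as worsening. Growth past 40 kg also lowers the count.
- Some Table 6 footnotes cannot be seen in the public text.

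**Conclusion.** The concern holds. The low-weight rule covers two of three OLE entry routes, and the uncovered route can include subjects with no previous exposure to CC-93538. For each omitted subject the shortfall is 90 minutes of required observation (90 instead of 180), four contacts, and a 56-day interval (42 to 70 with visit windows) in place of 14-day intervals (at most 24).

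This rests on reading entry during Maintenance as excluding Week 48 completion, as the plan's own lists do. How many subjects are affected is unknown and may be none. It is a gap in coverage and does not contradict Section 7.2.4; no endpoint, analysis or error rate is touched. The change is worth making because following the rule as written gives the less experienced subject the weaker protection.

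**What to change.** In Section 6.3.2 and Table 6 footnote e, replace the route condition with: any subject weighing ≥ 30 kg and < 40 kg at OLE entry, including entry after Maintenance Week 48. Keep the rest of the rule unchanged. Apply it regardless of earlier arm, because Section 7.2.4 still protects the blind at OLE entry. Section 7.2.4 itself needs no change.

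The cost is up to 30 more minutes at each of three doses and four contacts per subject, some of whom already have experience of the drug. If six subjects in the band all entered after Week 48, that is at most 6 × 90 = 540 minutes (9 hours) of observation and 6 × 4 = 24 contacts. Because the change adds required procedures, it also needs an amendment with ethics approval (Section 12.5) and, if the consent content is affected, re-consent (Section 12.3). It could be included in the next amendment.
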